Pilot Study Investigating the Effect of Tai Chi as Treatment for IBS-C

NCT: NCT04132804

Principal/Overall Investigator: [name], MPH

Funding: None

Version Date: September 22, 2020

I. Background and Significance

a.) Historical background

Irritable bowel syndrome (IBS) is a functional gastrointestinal disorder (FGID) characterized by abdominal pain and altered bowel habits. IBS is chronic and relapsing, causing significant reductions in health-related quality of life and work productivity. As the most commonly diagnosed gastrointestinal disorder, IBS affects between 4%-22% of the general population worldwide.² In the United States, the distribution is approximately equal among IBS with constipation (IBS-C), IBS with diarrhea (IBS-D), and IBS with a mixed bowel pattern (IBS-M). IBS is diagnosed in the absence of other medical causes with a pathogenesis mainly focused on abnormalities in gastrointestinal motility, visceral sensation, brain-gut interaction, and psychosocial distress. Therefore, treatment options for IBS are aimed at various action sites of the brain-gut axis through the use of pharmacotherapy and dietary/lifestyle changes. In the case of IBS-C, strong methodological evidence for various types of conventional pharmacotherapy, such as bulking agents, prokinetics, and antispasmodics, is lacking. With inadequate relief from IBS symptoms, many patients seek out complementary and alternative medicine (CAM) therapies which are medical practices that are not considered to be a part of conventional medicine.⁵ A subset of CAM therapies focuses on mind-body interventions. 6 In recognition of the communication between brain and gut, one such mind-body practice that may be beneficial for patients with IBS-C is the ancient practice of Tai Chi.

Tai Chi Chuan (taijiquan) or Tai Chi is a mind-body practice borne of Chinese philosophy and martial arts which has been practiced for centuries to promote deep relaxation, strengthened health, and to prevent injuries and illness. The principle behind the practice is that Tai Chi improves the circulation of blood and Qi (energy) throughout the body which enhances the body's natural healing capabilities. Tai Chi achieves this through gentle moving meditation and focusing on five building blocks: body, breath, mind, energy, and spirit. Through this method, Tai Chi practitioners exercise a balance between strength and flexibility, condition muscles, increase bone density, and massage their internal organs.⁷

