Through reinforcement of the mind-body connection, Tai Chi may be helpful in relieving chronic abdominal pain associated with IBS-C. The gentle moving meditation involved in Tai Chi practice may influence proper breathing and abdominal wall control in addition to massaging internal organs through movement.

Previous research has suggested that therapies engaging the mind-body connection may have promising effects on functional bowel disorders in general, and on IBS specifically. ^{18, 5} Some mind-body therapies, such as gut-focused hypnotherapy, have already gained approval as an effective treatment in reducing symptoms of IBS. ¹⁹ Similarly to already established mind-body therapies, Tai Chi may positively impact symptoms of IBS-C by changing sensory perception or even calming colonic motility. Tai Chi practice could lead to reduced abdominal distention and improved anxiety and depression scores.

II. Specific Aims

This is a single center pilot study. The purpose of the study is to evaluate the efficacy of Tai Chi practice in reducing symptoms of IBS. Patients who meet the Rome IV criteria for IBS-C and who meet the inclusion criteria will be offered participation in the study. We hypothesize that patients practicing Tai Chi will have reduced symptoms of IBS-C as measured through the Global Assessment of Relief, Irritable Bowel Syndrome Severity Scoring System (IBS-SSS), Irritable Bowel Syndrome Quality of Life (IBS-QOL), Visual Analogue Pain Scale, and abdominal distention. We also hypothesize that daily entries made through the GeoPain app will show a trend toward reduced pain intensity.

III. Subject Selection

This study aims to recruit 24 total subjects to be enrolled at one site, Massachusetts General Hospital. The 24 subjects that this study aims to recruit factors in a dropout rate of 15%, with a final sample size of 20 subjects.

INCLUSION/EXCLUSION CRITERIA:

Inclusion

- 1. Age 18 70 years
- 2. BMI \leq 35
- 3. Rome IV criteria for IBS-C
- 4. Continued IBS-C throughout run-in period
- 5. Compliant with reporting during run-in
- 6. Ability to follow verbal and written instructions
- 7. Ability to record daily patient reported outcomes via RedCap survey
- 8. Ability to use the GeoPain app on a smart phone
- 9. Ability to use Zoom as a platform for conducting study visits virtually
- 10. Ability to respond to 80% of the daily diaries
- 11. Ability to attend at least 7 out of 8 Tai Chi classes
- 12. Informed consent form signed by the subjects

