Exclusion

- 1. Unwilling to abstain from participation in Tai Chi (other than that provided for the study) or other mind-body practices (i.e. yoga that is new to regimen) until completion of the study
- 2. Non-English speaking
- 3. Participation in any other clinical trial with active intervention within the last 30 days
- 4. Non-compliance with reporting during run-in period (less than 80% completed REDCap and GeoPain entries)
- 5. Inability to stand without assistance for 20 minutes
- 6. Patients reporting any usage of a prohibited medication during the run-in period
- 7. History of regular opiate or narcotic pain-reliever use
- 8. Current use of prescribed or illicit opioids
- 9. Change in current medication regimen related to GI motility, laxatives, or antidepressants
- 10. Abdominal pain severity of 4 on a 0-4 visual analogue scale, where 4 is the worst possible pain, during pre-screen or run-in
- 11. Severe osteoarthritis
- 12. Severe rheumatoid arthritis
- 13. Severe constipation defined as <1 bowel movement per week without use of laxatives
- 14. History of GI lumen surgery (including gastric bypass) at any time or other GI or abdominal operations within 60 days prior to entry into the study
- 15. History of small bowel resection (except if related to appendectomy)
- 16. Subjects anticipating surgical intervention during the study
- 17. Angina, coronary bypass, or myocardial infarction within 6 months prior to Screening Visit
- 18. Crohn's disease or ulcerative colitis
- 19. History of intestinal stricture (e.g., Crohn's disease)
- 20. BMI >35
- 21. Pregnancy (or positive urine pregnancy test(s) in females of childbearing potential)
- 22. Known history of diabetes (type 1 or 2)
- 23. History of gastroparesis
- 24. History of abdominal radiation treatment
- 25. History of pancreatitis
- 26. History of malabsorption or celiac disease
- 27. History of intestinal obstruction or subjects at high risk of intestinal obstruction including

- suspected small bowel adhesions
- 28. History of human immunodeficiency virus
- 29. History of cancer within the past 5 years (except adequately-treated localized basal cell skin cancer or *in situ* uterine cervical cancer)
- 30. Neurological disorders, metabolic disorders, or other significant disease that would impair their ability to participate in the study

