 - 1. Record whether study participant verbally states they are pregnant or not for women of child-bearing potential (If restrictions are lifted and study visits are being performed on site, perform urine pregnancy test on women of child-bearing potential) (performed by research staff)
 - m. Self-reported leg strength assessment

2. Run-In Period

After a screening visit in which patient eligibility will be determined through use of the Rome IV IBS-C criteria along with other inclusion and exclusion criteria as above, there will be a 2-week run-in period. The 2-week run-in period may occur up to 3 months before the trial start date to facilitate accumulation of enough patients for a 10-person class.

Prohibited Medications

During this time no use of contraindicated medication per exclusion criteria will be allowed.

a. Opiate and narcotic pain-relievers

Permitted Medications at Stable Doses

The following medications are permitted as long as the medication dose has been stable for 3 months prior to the run-in period:

- a. Laxatives (e.g. linaclotide, lubiprostone, bisacodyl, senna, MiraLAX)
- b. Prokinetic medications (e.g. domperidone, metoclopramide, erythromycin, prucalopride)
- c. Antidepressant medications (e.g. SSRIs, SNRIs, TCAs, trazodone, bupropion)
- d. Neuromodulators (e.g. gabapentin, pregabalin, buspirone)

- e. Aluminum/Magnesium
- f. Calcium-channel blockers (e.g. amlodipine, diltiazem, nifedipine, nicardipine)

During the run-in period, subjects will be asked to complete a daily REDCap diary entry, a daily GeoPain entry, as well as complete the Visual Analogue Pain Scale, and turn in a stool sample within 2 weeks before the start of the treatment period. A stool kit may be mailed to subjects' homes, which subjects will then mail completed back to the research site.

Rescue Medications

If a subject does not have any documented bowel movement for 5 consecutive days and is in need of a rescue treatment, they will be asked to please contact the study doctor or study coordinator immediately. The study doctor will recommend the following rescue treatments, as applicable, in the following order:

- a. Laxatives: either MiraLAX or Dulcolax
- b. Glycerin suppository
- c. Enema

Administration of the rescue treatment will be at the discretion of the investigator based on their assessment of the subject's symptoms; administration of rescue treatment will be monitored and recorded.

3. Treatment Period (Day 0 to 49)

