One day prior to the treatment period, subjects will again complete the Rome IV questionnaire confirming that inclusion and exclusion criteria continue to be satisfied.

Subjects will be asked to refrain from making any major lifestyle changes (e.g. starting a new diet or changing their exercise pattern outside of Tai Chi practice) during the study.

During the treatment period, subjects will meet via Zoom once per week for one-hour Tai Chi lessons with an experienced instructor. A member of the research staff will send the password-protected Zoom invitation link to the subject's preferred email address via Send Secure or regular email, depending on the subject's preference. Subjects will also be instructed to practice Tai Chi at home outside of the lessons using the instructions, handouts, and guidance from the instructor.

Subjects will be instructed to complete a daily REDCap diary entry and a daily GeoPain entry to record information about stool frequency and consistency, abdominal bloating, abdominal discomfort, and abdominal pain. Subjects will also use the REDCap diary to report rescue medication use and daily Tai Chi practice.

The lessons will occur on Days 0, 7, 14, 21, 28, 35, 42, and 49. The Tai Chi lessons will take place remotely via Zoom. Should restrictions be lifted and study visits be performed on site, lessons will take place in the Simches Research Center at [name].

On Days 0, 21, and 49 subjects will be phoned by a member of the research staff for

assessments prior to their regularly scheduled Tai Chi lesson. Assessments will include vitals (if the study is operating on site only), weight, height, waist circumference, leg strength, and questionnaires. Assessments will be completed with research staff over the phone or, if restrictions are lifted and study visits are conducted on site, at the Center for Neurointestinal Healthcare at [name], after which subjects will go to their regularly scheduled Tai Chi lesson at Simches. Participants will also complete a qualitative survey over the phone with a member of the study staff that will be audio recorded and later transcribed in order to gain a full, complete, qualitative understanding of the patient's perspective of the investigational treatment that was used.

4. Post-Treatment Period (Day 77)

Subjects will complete a REDCap diary entry regarding symptoms 28 days post-treatment, 4 weeks after the final study visit.

5. Schedule of Events

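### For participants who wait for a class, the run-in diary can end up to 75–78 days before the first lesson, so change from run-in includes untreated time; the baseline stool timing also conflicts.

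*Combined protocol and SAP*

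**What the plan says.** **Timing.** A 2-week run-in follows screening. Section V.b.2 says: "The 2-week run-in period may occur up to 3 months before the trial start date", so that a class of 10 can be assembled. The Schedule of Events repeats the 3-month limit for both Screening and Run-In. Section VII.b plans two cycles of at least 10 participants.

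**Diary.** Daily REDCap and GeoPain entries are requested in the run-in. For the treatment period, Section V.b.3 says: "Subjects will be instructed to complete a daily REDCap diary entry and a daily GeoPain entry". No section asks for entries in between.

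**Endpoints and analysis.** Section V.b.7.b, item 5, gives run-in as the pre-treatment window for Bristol stool form and CSBM/SBM frequency. Item 7 lists daily bloating, discomfort and constipation scales without a baseline window. Section VII.a compares each participant before and after by paired t-test and treats the secondary endpoints similarly, without defining the before value. (Its cross-reference to V.a.6.b is read here as the list in V.b.7.b.)

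**Check before treatment.** One day before treatment, "subjects will again complete the Rome IV questionnaire confirming that inclusion and exclusion criteria continue to be satisfied".

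**Stool sample.** Among the run-in tasks, Section V.b.2 asks participants to "turn in a stool sample within 2 weeks before the start of the treatment period". The Schedule of Events marks the sample at Screening, Day 49 and Day 77, and leaves Run-In and Day 0 blank.

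**The concern.** The study has one arm, so a before/after difference is all it can report, and Section I.a itself says that "IBS is chronic and relapsing". If the before value comes from a run-in that ended weeks before the first lesson, any untreated change during the wait, better or worse, is added to the change seen under Tai Chi. The exposure differs between participants: someone who joins just before a class starts has no gap, while someone who joins early may have one longer than the 49-day treatment period.

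At stake are five secondary diary measures in a pilot meant to show trends for a larger trial. The stool question is separate: staff following the text and staff following the table would collect the pre-treatment sample at different times, and the microbiome comparison in Section VI depends on that sample.

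**Working it through.** **1. The plan's own figure.** Section III: 20 / (1 − 0.15) = 23.5, rounded up to 24. This reproduces. Below, n = 20 is the analysed sample and 24 the ceiling for burden.

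**2. Length of the gap.** Inputs from Section V.b.2: run-in 14 days, limit 3 months (89 to 92 calendar days).
- Longest gap: 89 − 14 = 75 to 92 − 14 = 78 days, about 11 weeks.
- Shortest gap: 0 days, if the run-in ends on Day −1.
- With a run-in starting 91 days before Day 0, the gap is 77 days. Of the time from end of run-in to Day 49, 77 / (77 + 49) = 61% is untreated.

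**3. Which measures are exposed.**

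| Measure | Pre-treatment values | Exposed in those who wait? |
|---|---|---|
| Bristol stool form, CSBM/SBM frequency | Run-in, named in V.b.7.b item 5 | Yes |
| Daily bloating, discomfort, constipation scales | Run-in is the only multi-day window; no baseline stated | Yes, if run-in is the baseline (inferred) |
| GeoPain | Run-in; a hypothesis in Section II, not listed in V.b.7 | Only if compared with run-in |
| IBS-SSS, the other before/after questionnaires, Visual Analogue Pain Scale, waist | Screening and Day 0 | No, if Day 0 is the baseline |

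The Day 0 diary mark is a single day and cannot give a weekly bowel-movement rate. The Schedule has no column for the wait, so its silence proves little; the stronger evidence is that no text requests entries then. Day 0 is also not named as baseline for the last row: V.b.7.b item 8 lists pre-treatment and visit 2 (Day 0) as separate times.

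**4. Illustration of size (assumptions only).** Suppose a fraction f of participants wait and their mean untreated change is d, in SDs of the change score. The paired mean is shifted by b = f × d. Hold the SD fixed and assume a two-sided 5% test, which the plan does not state. With n = 20, t(0.975, 19) = 2.093, so the 95% CI half-width is 2.093 / √20 = 0.468 SD. With no Tai Chi effect and noncentrality b√20:

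| Example | b | Significant results |
|---|---|---|
| nobody waits, or d = 0 | 0 | 5.0% |
| f = 0.5, d = 0.2 | 0.1 | 7.1% |
| f = 1, d = 0.2 | 0.2 | 13.6% |
| f = 1, d = 0.3 | 0.3 | 24.7% |

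**5. Stool timing.**
- *Text against table.* Screening comes before a 14-day run-in, so a Screening sample is at least 14 days before Day 0 and may be about 3 months before. It meets the 2-week window at its edge at best.
- *Within the text.* After a gap of w days, the run-in covers Days −(w + 14) to −(w + 1). This overlaps Days −14 to −1 only if w is 13 or less. From w = 14 on, no day is both within the run-in and within 2 weeks of treatment.

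**The case against.** **The flexibility is deliberate and the drift is constrained.** Section V.b.2 gives its reason. Eligibility is re-confirmed on Day −1, and the exclusions include "Change in current medication regimen related to GI motility, laxatives, or antidepressants". Participants must avoid other Tai Chi and new mind-body practice and are asked not to change diet or exercise, and concomitant medications are reviewed on Day 0. All this stands as a limit on some causes of drift. None of it supplies diary values, and it does not stop natural fluctuation.

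**The run-in baseline is partly inferred.** This stands for the three daily scales. Section V.b.3's account of diary content does not even mention constipation severity. It does not stand for stool form and frequency, where run-in is named.

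**Fluctuation is not bias.** A relapsing condition may add only noise; a mean shift is a further assumption. A reader might infer from the table of rates that the secondary results are inflated by a known amount, or in favour of Tai Chi. The documents give neither f nor d, nor a direction, and state no significance level.

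**The fix makes baselines less uniform.** Those who did not wait keep an eligibility-selected run-in; those who waited get an unselected window; poor compliers fall back on the old run-in and keep the gap. This stands. A sensitivity analysis discloses it but does not remove it.

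**Conclusion.** The concern holds for secondary diary endpoints. In participants who wait, change from run-in includes up to 75 to 78 untreated days. That is documented for stool form and CSBM/SBM frequency, and inferred for the three daily scales. How many wait, for how long, and the size and direction of any bias are unknown; if nobody waits or nothing drifts, the bias is zero.

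Stronger readings are not supported:
- *The primary result is compromised.* IBS-SSS is scheduled on Day 0. What is missing is a statement that Day 0 is its baseline.
- *The GeoPain endpoint is biased.* Section II hypothesises only that "daily entries made through the GeoPain app will show a trend toward reduced pain intensity"; it names no comparison with run-in.
- *A contiguous baseline would isolate the effect of Tai Chi.* It removes only change during the wait. Change over Days 0 to 49 remains uncontrolled.
- *Moving one mark in the Schedule settles the stool timing.* Section V.b.2 also conflicts with itself once the gap reaches 14 days.

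This is an inexpensive and worthwhile improvement, not a flaw that undermines the pilot.

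**What to change.** - **Diary baseline.** Keep the run-in for eligibility whenever it occurs. Participants whose run-in ended before Day −1 repeat the existing REDCap and GeoPain entries in the 14 days ending on Day −1, and that window becomes their diary baseline. State in Section VII.a that this applies to stool form, CSBM/SBM frequency and the three daily scales.
- **Completeness.** Do not re-apply the run-in 80% eligibility rule to the repeat window, and say how the window relates to the general 80% diary criterion in Section III. Set a minimum number of entries in advance; 7 of 14 is one suggestion. Below it, use the original run-in and flag the participant.
- **Reporting.** Record each wait in days. Give a sensitivity analysis with the original run-in as baseline for everyone. The change from run-in to repeat window can also be shown descriptively as an estimate of untreated change.
- **Other measures.** Name Day 0 as baseline for everything measured at both Screening and Day 0, including IBS-SSS.
- **Stool sample.** Reconcile Section V.b.2 and the Schedule so that the baseline sample is tied to the 2 weeks before Day 0, and not to the run-in or Screening.

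**Cost.** An IRB-approved amendment, class dates fixed at least 2 weeks ahead, and at most 24 × 14 = 336 diary plus 336 GeoPain entries, 672 in all. There is no extra visit or stool sample, and classes can still be filled flexibly.

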1. Patients agreeing to participate will sign an informed consent with the study physician or research coordinator at the time of enrollment, after proper informed consent has been provided by the site. Due to COVID-19 restrictions and social distancing, REDCap eConsent will take the place of written documentation of informed consent.

c.) Treatment Assignment

1. All patients will participate in 8 weeks of one-hour Tai Chi sessions once per week.

V. Study Procedures

a) Remote conduct of study visits and procedures

Due to COVID-19 and its restrictions, all eligibility screening and study visits listed below will be performed remotely until restrictions are lifted at the study site. All remote visits will be conducted over Zoom and the visit schedule will not change. All research staff will follow the MGH requirements for using Zoom (Enterprise Zoom as well as Healthcare Zoom- for any study visits involving patient care.) All questionnaires will be administered remotely via REDCap or over the phone. All Zoom link invites will be password protected and emailed by research staff to study participants using Send Secure or unencrypted email, depending on the subject's preference.

b.) Study visits and parameters to be measured

- 1. Eligibility Screen (to be conducted via Healthcare Zoom)
 - a. Obtain informed consent (performed by research staff)
 - b. Collect demographic data (performed by research staff)
 - c. Assessment of sufficient space to perform Tai Chi in-home (performed by research staff)
 - d. Assess inclusion/exclusion criteria (performed by research staff)
 - e. Rome IV questionnaire to screen for IBS-C (performed by research staff)
 - f. Collect medical and surgical history (performed by research staff)
 - g. Collect concomitant medications (performed by research staff)
 - h. Self report of height, weight, and waist measurement (if restrictions are lifted and study visits are being performed on site, vital signs will be recorded) (performed by research staff)
 - i. Perform brief physical examination by study physician
 - j. Visual Analogue Pain Scale (performed by research staff)
 - k. Questionnaires including Global Assessment of Relief, Hospital Anxiety and Depression Scale (HADS), Gastrointestinal Symptom Rating Scale-IBS version (GSRS-IBS), Irritable Bowel Syndrome-Behavioral Responses Questionnaire (IBS-BRQ), Fear of Food Questionnaire (FFQ), Visceral Sensitivity Index (VSI), IBS-SSS, and IBS-QOL(performed by research staff)

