Every session will include the following components: (1) Tai Chi warm ups with a strong emphasis on balance between strength and flexibility while reviewing Tai Chi principles; (2) Tai Chi breathing with self-massage (3) Tai Chi relaxation with meditation and visualizations (4) Tai Chi form which includes 10 moves from the Yang style Tai Chi (5) Tai Chi drills which are the Tai Chi individual postures practice (6) Tai Chi combination of movements and principles which are part of the Tai Chi philosophy. We will instruct patients to practice at least 30 minutes a day at home throughout the intervention period.

7. Data to be Collected and Timeline for Collection

- a. Primary endpoints
 - 1. IBS-SSS (pre-treatment, halfway point, and at conclusion of study)

b. Secondary endpoints

- 1. Likelihood of continuing treatment (5-point scale, end of study)
- 2. Treatment satisfaction (5-point scale, end of study)
- 3. Global Assessment of Relief and Visual Analogue Pain Scale (pre-treatment and each study visit)
- 4. Change of IBS-QOL, VSI, and HADS (pre-treatment, halfway point, and at conclusion of study)
- 5. For each BM: Bristol stool scale, stool frequency (CSBMs and SBMs; for each BM, during run-in and during study)
- 6. Waist circumference measurements (pre-treatment, halfway point, and at conclusion of study)
- 7. Daily: Bloating Scale, Abdominal Discomfort Scale, Constipation Severity Scale
- 8. Gastrointestinal Symptom Rating Scale-IBS version (GSRS-IBS), Irritable Bowel Syndrome-Behavioral Responses Questionnaire (IBS-BRQ), Fear of Food Questionnaire (FFQ) (pre treatment, study visit 2, and at conclusion of study)
- 9. Leg strength assessment patient (pre-treatment, halfway point, and at conclusion of study)
- 10. Instructor assessment as to confidence that patient has mastered technique (x1 at end of study, 5-point scale)
- 11. Client satisfaction questionnaire and qualitative survey (at conclusion of study)
- 12. Stool for metabolomics, and microbiome (pre-treatment and at conclusion of study)

8. Compliance

- a. Study coordinator will remind subjects of Tai Chi sessions and monitor completion of daily diaries, reports of home practice, and rescue medication use. Subject attendance will be monitored during each Zoom/in-person session by staff-completed attendance forms as well as class sign-in sheets. Number of missed sessions for each subject will be tracked.

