 Stool will be stored to check for metabalomics that may profile changes between the pre-treatment and treatment sample.
- 2. Microbiome Analysis
 Standard 16s rRNA sequencing for taxonomic identification and metagenomic profiling of the gut microbiome will be performed on stool samples to profile microbiome diversity and changes in microbiome between the pre-treatment and treatment sample.

VII. Biostatistical Analysis

- a.) Endpoint analyses
 - 1. Primary endpoint: IBS-SSS will be compared in a paired fashion for individual patients before and after the intervention using repeated measures t-test.
 - 2. Secondary endpoints: The secondary endpoints (as outlined in section V.a.6.b.) will be compared in a similar fashion.

b.) Power analysis

This is a single-center clinical exploratory pilot investigating the treatment of IBS-C using Tai Chi. As a pilot study, we hope to enroll 24 subjects with a final sample size of 20 subjects. The study will be conducted in two cycles of at least 10 subjects each to facilitate a full classroom size. Based on a previous pilot study involving Tai Chi as treatment for rheumatoid arthritis¹², 20 subjects appears to be a feasible number for detecting a trend toward outcomes that can be investigated in a future larger clinical trial.

VIII. Risks and Discomforts

a.) Tai Chi

Tai Chi is a relatively safe practice that is unlikely to cause injury if done with proper instruction. Caution should be exercised with conditions such as pregnancy, hernia, joint problems, and severe osteoporosis.

b.) Other Possible Risks

Other possible risks and side effects include skin irritation from inadvertently coming in contact with preservatives in the specimen collection materials, breach of confidentiality involving protected health information, and that information about taking part in a metabolic/microbiome study could influence insurance companies or employers regarding the patient's health. Study IDs will be utilized to minimize breaches of confidentiality. Filling out questionnaires could cause patients to feel uncomfortable.

IX. Potential Benefits

- a.) It is hypothesized that Tai Chi may be of benefit in patients with IBS-C. Potential benefits may include a decrease in self-reported abdominal pain/discomfort, straining, bloating, and constipation severity, as well as improved quality of life and symptoms severity.

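### Does taking the Day 49 IBS-SSS before the eighth and last Tai Chi lesson undermine the primary before-and-after comparison?

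*Combined protocol and SAP*

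**What the plan says.** Section IV.c (Treatment Assignment) defines the intervention: "All patients will participate in 8 weeks of one-hour Tai Chi sessions once per week". Section V.b item 3 (Treatment Period, headed Day 0 to 49) fixes the calendar: "The lessons will occur on Days 0, 7, 14, 21, 28, 35, 42, and 49". It also sets the assessment days: "On Days 0, 21, and 49 subjects will be phoned by a member of the research staff". The order within each of those days is explicit, since the call is for "assessments prior to their regularly scheduled Tai Chi lesson", and questionnaires are among those assessments. On-site conduct keeps the same order: assessments come first, "after which subjects will go to their regularly scheduled Tai Chi lesson".

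Section V item 7 lists the primary endpoint as "IBS-SSS (pre-treatment, halfway point, and at conclusion of study", with no study day. Section VII.a says the scores are "compared in a paired fashion for individual patients before and after the intervention", again with no study day. The Schedule of Events marks IBS-SSS at Screening, Day 0, Day 21, Day 49 and Day 77. That row lost columns when the PDF was read, but its five marks match the HADS and VSI rows. The Post-Treatment Period text mentions only a diary entry at Day 77.

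**The concern.** Read literally, a score taken before the last session does not come after an eight-session programme. IBS-SSS is the only primary endpoint, the study has one arm, and the primary analysis is specified in a single sentence. A label that does not match the data would therefore sit on the headline result. If benefit builds with exposure, the score would understate the change from the full programme. The only later IBS-SSS, at Day 77, comes four weeks after the last lesson and so measures persistence, not the end-of-treatment state.

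**Working it through.** **Which day is the later score?** Neither Section V item 7 nor Section VII.a says, so the indications have to be weighed.

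- For Day 49: there are three assessment days in the treatment period (0, 21, 49) and three named times for the primary endpoint.
- For Day 49: the midpoint of Days 0 to 49 is 49/2 = 24.5, which is 3.5 days from Day 21. The midpoint of Days 0 to 77 is 77/2 = 38.5, which is 17.5 days from it. Day 21 is a plausible halfway point only if the end is Day 49.
- For Day 49: "Client satisfaction questionnaire and qualitative survey (at conclusion of study" has the same timing label as the primary endpoint, and both items are marked at Day 49 only. The Post-Treatment Period text also counts its four weeks from the final study visit, which makes Day 49 that visit.
- For Day 77: stool collection carries the same end-of-study label but is marked at both Day 49 and Day 77. Treatment satisfaction and the instructor assessment, also labelled end of study, are marked on both days too. Section V (Adverse Events) runs participation to 28 days after the last treatment, and 49 + 28 = 77.

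Day 49 is the better reading, but the evidence is mixed.

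**Lessons before each IBS-SSS.** The lesson days come from Section V.b item 3, with the assessment placed before any lesson on the same day.

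| IBS-SSS day | Lessons already held | Days since previous lesson |
|---|---|---|
| Day 0 | 0 of 8 | none held yet |
| Day 21 | 3 of 8 | 21 − 14 = 7 |
| Day 49 | 7 of 8 | 49 − 42 = 7 |
| Day 77 | 8 of 8 | 77 − 49 = 28 |

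**Share of exposure missing at Day 49.**

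- Lessons only: 1/8 = 12.5%.
- Lessons plus home practice at the instructed minimum of 30 minutes a day (Section V item 6): home practice on Days 0 to 48 is 49 × 0.5 = 24.5 h, and seven lessons add 7 h, giving 31.5 h. With lesson 8 the total is 32.5 h, so the missing share is 1/32.5 = 3.1%.

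The two figures bracket the missing share: 12.5% if nobody practises at home, 3.1% if everyone meets the minimum, less if they exceed it. These are exposure counts, not effects on IBS-SSS. The documents hold nothing from which that effect could be derived.

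**What moving the score would do.** Suppose it were collected on Days 50 to 52. The gap since the last lesson becomes 1 to 3 days, against 7 at Day 21. The documents give no recall period for IBS-SSS. If 7 to 10 days is assumed, the part of the recall window after lesson 8 runs from 1/10 = 10% to 3/7 = 43%. Most of what participants report would still describe the days before lesson 8.

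**The case for a change.** The strongest case for a change does not depend on the size of the bias. Two pre-lesson scores (Screening, up to three months before treatment, and Day 0) and two candidate end scores (Day 49 and Day 77) allow 2 × 2 = 4 primary contrasts, and Section VII.a fixes none of them. If the Day 77 text overrides the schedule, no IBS-SSS follows lesson 8. The remedy looks cheap, because questionnaires already go out by REDCap or phone to only 20 to 24 people.

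Part of this stands. The days are not named, and the Day 77 text is thinner than the schedule. But the unnamed days are a separate matter from the order of assessment and lesson. The treatment period is headed Day 0 to 49, so an analyst would naturally pair Day 0 with Day 49. The Day 77 sentence does not say that the diary is the only procedure, and the schedule marks IBS-SSS and 18 other procedures that day. It is more likely an incomplete description than a withdrawal of the questionnaire.

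The remedy also costs more than it seems. IBS-QOL, VSI and HADS are collected on the same days and, under Section VII.a, analysed in like manner. Moving IBS-SSS alone would separate it from them and leave the same mismatch in place for them.

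It can be added that a participant who missed one of the first seven lessons would have had six by Day 49. That reflects attendance, not the schedule. Inclusion criterion 11 concerns the ability to attend, and such a participant can receive at most seven lessons, so the timing still leaves out only one.

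**Conclusion.** No change to the plan follows. On the Day 49 reading, the end-of-treatment IBS-SSS comes before one of eight lessons, which is 3.1% of instructed hours at the minimum home practice and at most 12.5%. If benefit grows with exposure, the effect is to understate the change, and it may be close to zero. Seven classes is also the attendance level that the eligibility criteria already accept. On the Day 77 reading, all eight lessons come first and the point does not arise.

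Measuring before the lesson is a fair trade-off. It gives an unexposed baseline at Day 0, equal 7-day gaps at Days 21 and 49, and a score free of the immediate effect of a session. Section VII.b describes an exploratory pilot looking for a trend and states no effect size, significance level or power, so no decision threshold depends on one lesson. The unnamed days and the short Day 77 text are gaps that analysts would fill sensibly: Day 0 against Day 49, Day 77 as follow-up, and a report that describes the Day 49 score as taken before the final lesson.

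This conclusion assumes that the lesson calendar and the order of assessment and lesson are followed as written, and that no single lesson carries an outsized share of any benefit. Nothing in the documents suggests that one does.
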